2.1 Study Outcome Measures as Related to Objectives

Primary Outcome Measure (POM):

POM 1.1: Proportion of infants with ≥ 1 apneic event in a 48-hour monitoring period after vaccination in the “vaccinated” group and a 48-hour monitoring period after randomization in the “unvaccinated” group.

Secondary Outcome Measures (SOM):

SOM 1.1: Average number of apneic episodes in a 48-hour monitoring period after vaccination in the “vaccinated” group and a 48-hour monitoring period after randomization in the “unvaccinated” group.

SOM 1.2: Average duration of apneic episodes in a 48-hour monitoring period after vaccination in the “vaccinated” group and a 48-hour monitoring period after randomization in the “unvaccinated” group.

SOM 1.3: Proportion of infants requiring any increase in respiratory support in a 48-hour monitoring period after vaccination in the “vaccinated” group and a 48-hour monitoring period after randomization in the “unvaccinated” group.

SOM 2.1: Proportion of infants with ≥ 1 severe cardiorespiratory event in a 48-hour monitoring period after vaccination in the “vaccinated” group and a 48-hour monitoring period after randomization in the “unvaccinated” group.

SOM 2.2: Proportion of infants requiring positive pressure ventilation in a 48-hour monitoring period after vaccination in the “vaccinated” group and a 48-hour monitoring period after randomization in the “unvaccinated” group.

Exploratory Outcome Measures (EOM):

EOM 1.1: Proportion of infants with fever in a 48-hour monitoring period after vaccination in the “vaccinated” group and a 48-hour monitoring period after randomization in the “unvaccinated” group.

EOM 1.2: Proportion of infants with hypothermia in a 48-hour monitoring period after vaccination in the “vaccinated” group and a 48-hour monitoring period after randomization in the “unvaccinated” group.

EOM 2.1: Average number of oxygen desaturation events in a 48-hour monitoring period after vaccination in the “vaccinated” group and a 48-hour monitoring period after randomization in the “unvaccinated” group.

EOM 2.2: Average number of bradycardia events in a 48-hour monitoring period after vaccination in the “vaccinated” group and a 48-hour monitoring period after randomization in the “unvaccinated” group.

EOM 2.3: Proportion of infants requiring blood culture for and/or antibiotics (intravenously or intramuscularly) in the setting of blood culture for sepsis evaluation in a 48-hour monitoring period after vaccination in the “vaccinated” group and a 48-hour monitoring period after randomization in the “unvaccinated” group.

EOM 2.4: Proportion of infants with a serious adverse event in a 48-hour monitoring period after vaccination in the “vaccinated” group and a 48-hour monitoring period after randomization in the “unvaccinated” group.

EOM 3.1: Proportion of hospitalized infants with ≥ 1 episode of clinical apnea between 48 hours and 14 days after vaccination.

EOM 3.2: Proportion of hospitalized infants requiring any increase in respiratory support between 48 hours and 14 days after vaccination.

EOM 3.3: Proportion of hospitalized infants requiring blood culture and/or antibiotics (intravenously or intramuscularly) in the setting of blood culture for sepsis evaluation in between 48 hours and 14 days after vaccination.

EOM 3.4: Proportion of hospitalized infants requiring positive pressure ventilation in between 48 hours and 14 days after vaccination.

EOM 3.5: Proportion of discharged infants readmitted to the hospital within 14 days of vaccination.

3 STUDY DESIGN

This study is a prospective, randomized, open-label clinical trial to assess apnea in the 48 hours after randomization (“unvaccinated” group) versus 48 hours after vaccination (“vaccinated” group) with 13-valent Conjugate Pneumococcal Vaccine (PCV13), Diphtheria Toxoid, Tetanus Toxoid, and Acellular Pertussis Vaccine (DTaP), Hepatitis B vaccine (HBV), Inactivated Polio Vaccine (IPV), and *Haemophilus influenzae* Type B Vaccine (Hib) vaccines in premature infants <33 weeks and 0 days gestation at birth who have been hospitalized since birth and eligible to receive 2-month vaccines per the ACIP schedule.³⁰

At least 300 infants will be enrolled over a period of 28 months at Duke University (Duke), University of North Carolina at Chapel Hill (UNC) and Cincinnati Children’s Hospital Medical Center (CCHMC). The first 12 infants (Duke: 4, UNC: 4, CCHMC: 4) will be enrolled in a pilot study to assess the feasibility of the protocol and study instruments. The remaining 288 will be enrolled after the pilot study; 86 infants at Duke, 86 infants at UNC and 116 infants at CCHMC.

On day 1, eligible infants will be randomized 1:1 to a “vaccinated” or “unvaccinated” group. Infants in the “vaccinated” group will be continued on cardiorespiratory and pulse oximetry monitoring and PCV13, DTaP, HBV, IPV, and Hib vaccines will be given within 6 hours of randomization. Vaccines will be administered per ACIP recommendations.² Infants in the “unvaccinated” group will be continued on cardiorespiratory and pulse oximetry monitoring and no vaccines will be administered. Continuous cardiorespiratory and pulse oximetry monitoring

are standard of care procedures for infants hospitalized in NICU. The study will collect data from the continuous cardiorespiratory and pulse oximetry monitors from randomization to 48 hours after randomization for infants in the unvaccinated group, and from randomization to 48 hours after vaccination for infants in the vaccinated group. Blinded analyst(s) at Duke University will evaluate data recorded by the cardiorespiratory and pulse oximeter monitors during this time period to determine the occurrence of apnea, bradycardia, and desaturation. In addition, information will be collected on increased respiratory support, sepsis evaluation and serious adverse events.

For infants in the “vaccinated” group, the study will also collect adverse events of clinical interest and serious adverse events occurring between the end of the 48-hour monitoring period and 14 days after vaccination. This information will be collected through parental report and review of medical records.

4 STUDY ENROLLMENT AND WITHDRAWAL

Subject Inclusion and Exclusion Criteria will be reviewed at Day 1 to assess eligibility for study participation.

4.1 Subject Inclusion Criteria

Subjects who meet all of the following criteria will be eligible to participate in this study.

1. <33 and 0 days weeks gestational age at birth
2. ≥6 weeks and 0 days and ≤12 weeks and 0 days postnatal age at randomization
3. Remains hospitalized after birth (has never been discharged home)
4. Treating clinician deems infant eligible to receive 2-month vaccines
5. English- or Spanish-speaking parent(s)/legally authorized representative(s) (LAR(s))
6. Not planned for discharge within 60 hours of study entry
7. The parent/guardian must be willing to provide permission for their child to participate through the written informed consent process

4.2 Subject Exclusion Criteria

Subjects who meet any of the following criteria will not be eligible to participate in this study:

1. Receipt of DTaP, IPV, PCV13, or Hib prior to enrollment. Previous administration of the first dose of HBV is permitted
2. Anticipated receipt of any vaccine other than DTaP, IPV, HBV, PCV13, or Hib during the first 60 hours after randomization
3. History of a severe allergic reaction (e.g. anaphylaxis) to a previous dose of any hepatitis B vaccine
4. History of a severe allergic reaction (e.g. anaphylaxis) to any component of the vaccines used in the study including neomycin, yeast and polymyxin B
5. History of latex allergy
6. Fever ≥38°C within 48 hours prior to randomization*
**This may result in a temporary delay of randomization*
7. Active known respiratory infection within 48 hours prior to randomization*
**This may result in a temporary delay of randomization*
8. Active infection being treated with systemic antimicrobials*
**This may result in a temporary delay of randomization*
9. Requiring mechanical ventilation or support with nasal intermittent positive pressure ventilation (NIPPV)*
**This may result in a temporary delay of randomization*
10. History of unstable progressive neurologic disorder of unknown cause
11. Known cause of apnea other than apnea of prematurity
12. Cyanotic heart disease (congenital or acquired)

13. Major invasive medical or surgical procedure (including circumcision) within 48 hours prior to randomization or anticipated to have major invasive medical or surgical procedure during the first 60 hours after *randomization**
**This may result in a temporary delay of randomization*
14. Child or parent/LAR is an immediate relative of study staff or an employee who is supervised by study staff.
15. Any condition that would, in the opinion of the site investigator, place the participant at an unacceptable risk of injury or render the participant unable to meet the requirements of the protocol

4.3 Recruitment

Participants will be recruited from Duke, UNC and CCHMC. Infants hospitalized in the NICU will be screened for eligibility daily by study staff. Parent(s)/LAR(s) of the infants will be approached for consent. Infants' parent(s)/LAR(s) may be approached for consent when the infant is eligible to receive 2-month vaccines, or for pre-consent prior to being eligible to receive 2-month vaccines. Initial discussions regarding the study may occur over the phone (see section 5.2), but written informed consent will be obtained prior to any study procedures. The clinical care team will be consulted prior to approaching parents (LARs) for consent.

4.4 Reasons for and Handling of Withdrawals

The following may be reasons for study withdrawal:

- As deemed necessary by the principal investigator (PI).
- Parent(s)/LAR(s) withdrawal of permission for their infant to participate.
- Loss to follow-up.
- Termination of the study by the sponsor.

A parent/LAR may withdraw permission for their infant to participate at any time and for any reason, without penalty. Subjects who are withdrawn from the study prior to randomization will be replaced. Subjects who are withdrawn from the study after randomization will not be replaced. For subjects who were randomized, data collected prior to withdrawal from the study will be included in the study.

4.5 Termination of Study

This study may be terminated for safety concerns of the principal investigators from any of the enrolling sites, the CDC, or participating Institutional Review Boards (IRBs).

5 STUDY SCHEDULE, PROCEDURES, & EVALUATIONS

5.1 Study day definitions

Table 3. Study Day definitions		
	Vaccinated group	Unvaccinated group
Day 1	R → V + 23:59 hours:minutes	R → R + 23:59 hours:minutes
Day 2	V + 24 hours → V + 47:59 hours:minutes	R + 24 hours → R + 47:59 hours:minutes
Day 3	V + 48 hours → V + 95:59 hours:minutes	
Day 4	V + 96 hours → V + 119:59 hours:minutes	
Day 5	V + 120 hours → V + 143:59 hours:minutes	
Day 6	V + 144 hours → V + 167:59 hours:minutes	
Day 7	V + 168 hours → V + 191:59 hours:minutes	
Day 8	V + 192 hours → V + 215:59 hours:minutes	
Day 9	V + 216 hours → V + 239:59 hours:minutes	
Day 10	V + 240 hours → V + 263:59 hours:minutes	
Day 11	V + 264 hours → V + 287:59 hours:minutes	
Day 12	V + 288 hours → V + 311:59 hours:minutes	
Day 13	V + 312 hours → V + 335:59 hours:minutes	
Day 14	V + 336 hours → V + 359:59 hours:minutes	

R = time of randomization. V = time of vaccination. If infants in the vaccinated group are not vaccinated, then “V” should be replaced by “R + 12 hours”. Note that for vaccinated group, “Day 1” will be longer than 24 hours.

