 - a. *Definition:* Increase in mode of respiratory support will be defined as progression from any lower level at baseline (at time of randomization in the unvaccinated group and vaccination in the vaccinated group) to any higher level (**Figure 2**). In addition, any increase in nasal cannula flow rate, or continuous positive airway pressure (CPAP) will be considered an increase in mode of respiratory support.
 - b. *Method of collection:* Respiratory data will be collected from the EHR daily, and the highest level of support that is maintained for >1 hour will be recorded. In addition, start/stop date/time for NIPPV and mechanical ventilation will be recorded.
 3. Severe cardiorespiratory event (SOM 2.1)
 - a. *Definition:* Respiratory pause of >30 seconds in duration or bradycardia of <60 beats per minute for >10 seconds
 - b. *Method of collection:* Obtained from the cardiorespiratory monitor as described above.
 4. Positive pressure ventilation delivered via bag-valve mask (SOM 2.2)
 - a. *Definition:* Infant with unexpected clinical decompensation requiring positive pressure ventilation via bag-valve mask.
 - b. *Method of collection:* Obtained from the EHR as documented by a clinical provider (e.g., physician, nurse, respiratory therapist).
 5. Fever (EOM 1.1)
 - a. *Definition:* Elevated temperature $\geq 38^{\circ}\text{C}$.
 - b. *Method of collection:* Highest daily temperature will be recorded from the EHR, in addition to how the temperature was obtained (skin, axillary, rectal, etc.) and infant's environment (open crib, radiant warmer or isolette).
 6. Hypothermia (EOM 1.2)
 - a. *Definition:* Decreased temperature $< 36^{\circ}\text{C}$.
 - b. *Method of collection:* Lowest daily temperature will be recorded from the EHR, in addition to how the temperature was obtained (skin, axillary, rectal, etc.) and infant's environment (open crib, radiant warmer or isolette).
 7. Oxygen desaturation (EOM 2.1)
 - a. *Definition:* Oxygen desaturation will be defined as a $\text{SpO}_2 < 88\%$ for >10 seconds.
 - b. *Method of collection:* Obtained from the cardiorespiratory monitor as described above.
 8. Bradycardia (EOM 2.2)
 - a. *Definition:* Bradycardia will be defined as a heart rate <80 beats per minute lasting >10 seconds.

- b. *Method of collection*: Obtained from the cardiorespiratory monitor as described above.
- 9. Blood culture for sepsis evaluation (*EOM 2.3*)

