6.6 Analysis Plan

6.6.1 Pilot Study

The pilot phase of the study will include 12 infants. There will not be any formal analysis of study data. However, the feasibility benchmarks listed in **Table 5** will be documented for the first 12 patients to assess protocol adherence. These subjects will contribute to the final sample for analyses in the study objectives.

Table 5: Benchmarks for Pilot	
Benchmark	Target
Among pre-screened and eligible, LARs approached for consent	70%
Among approached for consent, consent obtained	40%
Documentation of reason for non-consent (of those approached)	80%
Among consent obtained, percent randomized	80%
Administration of vaccines in the vaccination group within 6 hours of randomization	60%
Administration of vaccines in the vaccination group within 12 hours of randomization	80%
Entire 48-hour monitoring period assessed for apnea events	80%

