Exploratory Objective 1 - To compare proportions of preterm infants with temperature instability in a 48-hour monitoring period after vaccination in the “vaccinated” group versus a 48-hour monitoring period after randomization in the “unvaccinated” group.

For this objective we will present the proportion of infants the proportion of infants in each group experiencing fever and the proportion in each group experiencing hypothermia (as defined in Section A.5.3) at least once during the 48 hours after randomization/vaccination and compare these proportions using a Mantel-Haenszel statistic.

Exploratory Objective 2 - To compare proportions of preterm infants with other clinically important adverse events in a 48-hour monitoring period after vaccination in the “vaccinated” group versus a 48-hour monitoring period after randomization in the “unvaccinated” group.

For this objective we will present the proportion of infants the proportion of infants in each group experiencing other clinically important adverse events (as defined in Section A.5.3) at least once during the 48 hours after randomization/vaccination and compare these proportions using a Mantel-Haenszel statistic. We will repeat these analyses for serious adverse events. We will report SAE narratives and relatedness descriptions (see section 5.3).

Exploratory Objective 3 - To compare clinically important adverse events occurring between 48 hours and 14 days after vaccination among infants in the vaccinated group who do, and do not have apnea in a 48-hour monitoring period after vaccination.

For this objective we will present the proportion of infants in the vaccinated group with and without apnea in a 48-hour monitoring period who experience each of these clinically important adverse events (as defined in section A.5.3) at least once between 48 hours and 14 days after vaccination. These subgroup comparisons will be conducted a Fisher’s Exact Test at the alpha 0.05 level.

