### 8.3 Exploratory Objectives

There are three exploratory objectives for this study.

- a) The first exploratory objective (**EO-1**) is to compare proportions of preterm infants with temperature instability in a 48-hour monitoring period after vaccination in the “vaccinated” group versus a 48-hour monitoring period after randomization in the “unvaccinated” group.

For this objective we will present the proportion of infants in each group experiencing fever (temperature  $\geq 38^{\circ}\text{C}$ ) (EOM 1.1) and the proportion in each group experiencing hypothermia (temperature  $< 36^{\circ}\text{C}$ ; as defined in **Section 5.4**) (EOM 1.2) at least once during the 48 hours after randomization/vaccination. These proportions (fever and hypothermia) will be compared using a Mantel-Haenszel statistic in a stratified analysis by study site and gestational age to control for the randomization blocks. The stratified odds ratio and corresponding 95% confidence interval for the occurrence of fever and hypothermia will also be calculated.

- b) The second exploratory objective (**EO-2**) is to compare event counts and proportions of preterm infants with other clinically important adverse events in a 48-hour monitoring period after vaccination in the “vaccinated” group versus a 48-hour monitoring period after randomization in the “unvaccinated” group.

For this objective the number of oxygen desaturation events (EOM 2.1) and the number of bradycardia events (EOM 2.2) will be presented using summary statistics regarding the number of distinct events and the duration of events, including mean, median, standard deviation, and range will be reported by group and site. The number of events for each outcome will be compared using a Poisson regression model with study site and gestational age as covariates to control for the randomization blocks.

The proportion of infants in each group experiencing other clinically important adverse events (infants requiring blood culture and/or antibiotics (intravenously or intramuscularly) in the setting of blood culture for sepsis evaluation (EOM 2.3) and infants with a serious adverse event (SAE; EOM 2.4; protocol section 5.4) at least once during the 48 hours after randomization/vaccination will be presented. These

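### Study-day numbering does not fit the 48 h to 14 day window of EO 3, and untimed readings leave the start of the vaccinated arm's 48-hour window unclear

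*Protocol*

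**What the plan says.** R is randomization and V is vaccination, as in Protocol 5.1.

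*Later period.* EO 3 and its outcome measures (Protocol 2 and 2.1; SAP 2.3, 3.3 and 8.3) cover 48 hours to 14 days after vaccination. The study-day Table 3 in Protocol 5.1 (the procedures table in 5.2 carries the same number) gives Day 3 as V+48 to V+95:59, then 24 h per day, ending with Day 14 at V+336 to V+359:59. Protocol 5.2 and the follow-up section 5.5 call the period days 3-14 and start it at V+48 h. Protocol 5.4 Data Collection, where the later events are defined, and 7.6 call it days 4-14. Section 5.4 also places the EOM 3.2 baseline on day 3, at the close of the study period.

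*First 48 hours.* The mITT population is primary (Protocol 6.6.2.1; SAP 6.2 and 6.4). In the vaccinated group it counts V to V+48 h, or R+12 to R+60 h if vaccination has not happened by 12 h. For fever and hypothermia, Protocol 6.2.2.3 counts infants affected "at least once during the 48 hours after randomization/vaccination and compare these proportions using a Mantel-Haenszel statistic", and SAP 8.3 keeps that window. Collection starts earlier: Protocol 5.4 collects days 1-2 events from R in both groups, and the study-day table starts vaccinated Day 1 at R, with the remark "Note that for vaccinated group, “Day 1” will be longer than 24 hours".

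Fever and hypothermia (EOM 1.1, 1.2) rest on one highest and one lowest temperature per day. Route and environment are recorded; a time is not mentioned. For respiratory support (SOM 1.3), "Respiratory data will be collected from the EHR daily, and the highest level of support that is maintained for >1 hour will be recorded". Times are named only for the top levels: "In addition, start/stop date/time for NIPPV and mechanical ventilation will be recorded". An increase is defined as "progression from any lower level at baseline (at time of randomization in the unvaccinated group and vaccination in the vaccinated group". Bag-mask ventilation (SOM 2.2, and EOM 3.4 later) is taken from the EHR, again with no time mentioned.

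**The concern.** Two separate things go wrong.

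First, the day labels for the later period contradict one another and the endpoint. A site abstracting by study day would use a different stretch of time from one abstracting by hours since vaccination. The EOM 3.2 baseline could be V+48 h or V+96 h. A rise in support between those times is an event under one baseline and part of the baseline under the other.

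Second, a daily extreme with no time attached, taken over a day that includes R to V, does not show on which side of vaccination it fell. The unvaccinated arm has no such interval. If the table's day is used, any stray counts fall in the vaccinated arm alone, which in a vaccine safety trial means a spurious push towards harm.

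**Working it through.** **The plan's own power figure.** With 15% against 30% and 135 per group, the pooled SE is sqrt(2 × 0.225 × 0.775/135) = 0.0508 and the unpooled SE is sqrt((0.1275 + 0.21)/135) = 0.0500. Power = Φ((0.15 − 1.96 × 0.0508)/0.0500) = Φ(1.008) = 84.3%, as stated. Nothing below changes it.

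**Later period, from the table's boundaries in hours after V**

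| Description | Span | Length |
|---|---|---|
| EO 3, 48 h to 14 days | 48 to 14 × 24 = 336 | 288 h |
| Table days 3-14 | 48 to 360 | 312 h |
| Table days 4-14 | 96 to 360 | 264 h |

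Day 3 lasts 96 − 48 = 48 h. Day 14 starts at 336 h, exactly where the EO 3 window closes. Table days 4-14 omit V+48 to V+96 h and add V+336 to V+360 h. Day 2 ends at V+47:59, so the 48-hour period is already over when Day 3 begins.

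Blood cultures and antibiotics have a date and time, readmission has a date, and clinical apnea is timed when nursing notes allow. These can be cut to the window whatever the label. That leaves mainly EOM 3.2 and EOM 3.4.

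**First 48 hours.** With lag L from R to V, the table's Days 1-2 span 48 + L hours in the vaccinated group against 48 h in the unvaccinated group: 54 h at L = 6 and 60 h at L = 12.

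The documents give no rates for fever or hypothermia. Assume a 48-hour risk p of 5% or 10%, constant hazard, no vaccine effect, and Day 1 taken as in the table. Then risk = 1 − (1 − p)^((48 + L)/48).

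| L, all infants | p = 5% | p = 10% |
|---|---|---|
| 3 h | 5.30%, OR 1.06, +0.41 per 135 | 10.59%, OR 1.07, +0.80 |
| 6 h | 5.61%, OR 1.13, +0.82 | 11.18%, OR 1.13, +1.59 |
| 12 h (extreme) | 6.21%, OR 1.26, +1.63 | 12.34%, OR 1.27, +3.16 |

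For a plausible lag mix, use the pilot targets in Protocol 6.6.1: 60% for "Administration of vaccines in the vaccination group within 6 hours of randomization" and 80% for "Administration of vaccines in the vaccination group within 12 hours of randomization". If these are just met and the remaining 20% are set to R+12 h, the mean lag is:

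- lowest: 0.6 × 0 + 0.2 × 6 + 0.2 × 12 = 3.6 h
- mid-interval: 0.6 × 3 + 0.2 × 9 + 0.2 × 12 = 6.0 h
- highest: 0.6 × 6 + 0.4 × 12 = 8.4 h

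Averaging the risk over these mixes adds 0.49, 0.82 and 1.15 infants per 135 at p = 5%, and 0.95, 1.59 and 2.22 at p = 10% (OR 1.08 to 1.19). At mid-interval the shift is 0.61 or 1.17 percentage points. The SE of a difference, sqrt(2p(1 − p)/135), is 2.65 or 3.65 points, so the shift is 0.61/2.65 = 0.23 or 1.17/3.65 = 0.32 of one SE.

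SOM 1.3 and SOM 2.2 are not quantified. The documents give no rate of weaning or of transient rises in support before vaccination, and none for bag-mask ventilation.

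**The case against.** On the later period, the objectives, endpoints and SAP analysis of EO 3 are all written in hours and days since vaccination, and two protocol sections start the period expressly at V+48 h. The day-3 baseline can be read as the end of the 48-hour period, which falls on the third calendar date. This shows what was probably meant. It does not remove the conflict, because the table, the days 4-14 labels and the baseline wording are all current text. A reader might infer that V+48 to V+96 h goes uncollected. The documents do not show that, since other sections cover those hours.

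On the first 48 hours, the counting rule is clear and repeated, and collecting from R is deliberate because the ITT window runs R to R+48 h. Several stronger readings are tempting but unsupported:

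- *The data cannot be cut at vaccination.* This argues from silence. The collection forms are not among the documents, and the EHR or the forms may hold times.
- *Daily means whole calendar dates, so hours outside the window enter in both arms.* That conflicts with the collection window in Protocol 5.4, which runs from R to 48 h after R or V.
- *SOM 1.3 is biased.* The definition already requires progression from the level at vaccination, so support that was higher only before V is not an increase. The exposure is limited to an untimed Day 1 maximum compared mechanically with that baseline.

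The size is also open to challenge, and fairly. Fever of 38°C or more in the 48 h before randomization is an exclusion, so the fever hazard just after R may be below average; hypothermia has no such criterion. The pilot targets are minimum benchmarks, while Protocol 5.2 plans vaccination within 6 h. Both points suggest the smaller figures.

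**Conclusion.** The later-period numbering is wrong as written and needs correcting. Day 14 lies wholly outside the EO 3 window, the two labels give 312 h and 264 h against 288 h, and the EOM 3.2 baseline does not match the table. These follow from the text without any assumption. The consequence is limited to an exploratory comparison within the vaccinated arm, so it is inconsistency and not bias between arms.

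The first-48-hour gap is a cheap improvement. It touches EOM 1.1, EOM 1.2, SOM 2.2 and the untimed part of SOM 1.3. It matters only if *daily* is taken as the table's day and no times are held, and neither is settled by the documents. For fever or hypothermia the size is then about 0.4 to 3.2 extra infants per 135 (OR about 1.06 to 1.27), or 0.2 to 0.3 of one SE at a 6 h mean lag. This rests on the assumed 5-10% risks, constant hazard and lags of 3-12 h.

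A reader might carry this over to the primary result. That would be mistaken: monitor events are recorded with date, time and duration, so apnea and every other monitor-based outcome can be cut exactly at V.

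**What to change.** *Later period.* In the Protocol 5.1 table, make every study day after Day 1 24 h long. Day 3 becomes V+48 to V+71:59 and Day 14 becomes V+312 to V+335:59, so Days 3-14 total 12 × 24 = 288 h, matching EO 3. Change days 4-14 to days 3-14 in Protocol 5.4 and 7.6. State the EOM 3.2 baseline as V+48 h. This costs wording only.

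*First 48 hours.* Record the date and time of temperatures crossing the fever or hypothermia threshold, of increases in support, and of bag-mask ventilation. Add one SAP sentence: mITT and PP count only those from V to V+48 h (keeping the existing R+12 h substitution in the mITT), and any ITT analysis counts R to R+48 h. Giving R to V its own day label would serve the mITT but not the ITT, whose window closes partway through the vaccinated group's Day 2; event times serve both.

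The cost is slightly more chart abstraction, or the SAP sentence alone if the forms already hold the times. No extra infants and no change to the primary analysis are needed.
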